#### 5.5.3 Duration of sustained response off treatment

This parameter is calculated as interval from discontinuation of treatment (including this day) until the date of the first measurement after treatment discontinuation with platelets < 30 G/l, i.e. the loss of response.

The following censoring rules are applied:

- If a patient does not loose sustained response the interval is censored with the date of the last platelet assessment
- If a patient does not respond initially (i.e. all platelet counts <30 G/L until treatment discontinuation) the interval is censored with 0 (days)

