Patients who relapse (< 30×10 ⁹ /L) after eltrombopag discontinuation before Week 52	Re-initiate treatment with eltrombopag with a starting dose of 50 mg/day till Week 52 and discontinue from study at Week 52	

Treatment in the control arm consists of 1-3 cycles of high-dose dexamethasone administered orally at a dose of 40 mg QD for 4 consecutive days at 4 weeks intervals (dexamethasone can also be given at 14 to 28 days intervals if needed according to current ITP guidelines). If the platelet counts are $> 150 \times 10^{9}$ /L no further course of dexamethasone will be given. Patients will be treated up to 12 weeks (3 months) during the treatment period with dexamethasone. Patients who reach platelet counts $\ge 30 \times 10^{9}$ /L and maintain counts $\ge 30 \times 10^{9}$ /L after 1-3 cycles of high-dose dexamethasone treatment will be eligible for treatment discontinuation. Patients with platelet counts $< 30 \times 10^{9}$ /L after 3 cycles of dexamethasone treatment will be offered a course of eltrombopag treatment within the study and will discontinue the study after completion of treatment with eltrombopag at Week 52 (Table 6-2).

Table 6-2Dexamethasone dosing guidance for patients not meeting criteria for
sustained remission

Platelet Level	Dose Guidance
Patients with platelet count < 30×10 ⁹ /L after 3 cycles with dexamethasone	Initiate treatment with eltrombopag with a starting dose of 50 mg/day and continue treatment with eltrombopag till Week 52 after study start and discontinue from study at Week 52
Patients who relapse (platelet count < 30×10 ⁹ /L) after dexamethasone discontinuation before Week 52	Initiate treatment with eltrombopag with a starting dose of 50 mg/day till Week 52 after study start and discontinue from study at Week 52

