8.3 Efficacy

The efficacy objective is to compare the ability of eltrombopag in combination with a short course of high-dose dexamethasone to a defined course of high-dose dexamethasone to induce sustained response off treatment at Week 52.

8.3.1 Efficacy assessment 1

Platelet count will be assessed at screening visit to assess the eligibility of the subject. Hematology including platelet counts will be performed at Week 1/Day 1 (baseline) and weekly

during the first 4 weeks of treatment. Based on subject's response, hematology will be performed biweekly thereafter until Week 33 Day 1 and every 4 weeks till Week 53 Day 1.

Additional assessments of platelet count may be performed more frequently if needed in accordance with the clinical judgment of the investigator as part of clinical routine.

8.3.2 Efficacy assessment 2

Bleeding events will be assessed at each visit and recorded in the AE CRF and in addition on an unique CRF for bleeding events. Documentation of the use of any rescue therapy will be documented on the appropriate CRF.

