#### 2.5.4 Supportive analyses

Novartis

Reasons for non-response are assessed during the Data Review Meeting and are categorized into these distinct categories:

- 1. Initial response but lost later on, or bleeding, or rescue medication before treatment discontinuation
- 2. Initial response but treatment not discontinued
- 3. Initial response but after treatment discontinuation rescue needed
- 4. Initial response but after treatment discontinuation bleeding
- 5. Initial response but platelet count decreased <30 after treatment discontinuation
- 6. Initial response but response data are missing until W53
- 7. No response at all
- 8. No response data at all

If several reasons apply, the reason that applied first was determined to obtain distinct classes. A frequency table was presented for these reasons of non-response.

Sensitivity analyses and supportive analyses will be conducted in order to provide evidence that the results seen from the primary analysis are robust.

The impact of the analysis assumptions on the result of sustained response off treatment will be assessed as well by repeating the logistic regression model using different populations and ways to handle missing data. These includes:

Using the treatment policy estimand "sustained response based on platelet count only" a) which is defined as maintenance of a platelet count  $\geq 30 \times 10^{9}$ /l starting from cycle 1, 2 or 3 (DEX), or start of tapering at week 20 (ETB+DEX), until Week 53, i.e. no matter if intercurrent events such as bleeding, treatment discontinuation or reinitiation, or rescue treatment occurred. For this estimand the population is used: Patients of the FAS population

b) Using the treatment policy estimand b) for the population: FAS population who completed the study at least until Week 53

Data defining the primary outcome of sustained response off treatment will be further reported descriptively to give the full picture. This will include:

- Platelet counts at treatment discontinuation: sample statistics
- Frequency of patients with complete response at treatment discontinuation; defined as a) platelet count  $\geq 150 \times 10^{9/1}$ 
  - b) platelet count >  $100 \times 10^{9/1}$
  - c) platelet count  $\geq 50 \times 10^{9/1}$
- Timepoint of reaching platelet count  $\geq 150 \times 10^{9}$ /l: Kaplan Meier estimates and curve, censored with date of last study medication/last visit

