# 5 Appendix

### 5.1 Derivation of time point of treatment discontinuation

The time point of **treatment discontinuation** is the date of last dose of study medication given as study treatment but not as rescue medication, not after re-initiation or not after as initial dose after failure of 1-3 DEx cycles, and not as concomitant medication (if applicable).

For patients randomized to DEX monotherapy the time point of treatment discontinuation is the date of last study medication dexamethasone documented on the "End of Treatment" CRF. During the data review meeting it will be verified, that this date corresponds to the stop of study treatment but not to the stop of rescue medication.

For patients randomized to ETX+DEX combination therapy the time point of treatment discontinuation is the maximum date of the study medications eltrombopag and dexamethasone documented on the "End of Treatment" CRF, in general. When the primary reason for permanent discontinuation of eltrombopag is:

- "stop of eltrombopag re-initiated after relapse", or
- "stop of eltrombopag as rescue medication for patients randomized to DEX monotherapy" or
- the free text specification of "other reason" indicate that elthombopag was re-initiated or used after switch from DEX to ETB

the stop of study treatment eltrombopag has to be visually assessed from the data of the "Eltrombopag – Dosage Administration Form" during the data review meeting.

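### SAP 5.5.3 can censor a sustained one-cycle DEX responder at 0 days, because initial response is judged before any post-dose platelet count is scheduled

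*SAP*

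**What the plan says.** Secondary endpoint 2 is the median duration of sustained response off treatment, estimated by Kaplan-Meier from the last dose of study treatment until loss of response (SAP 2.7.1, item 2). SAP 5.5.3 gives the derivation. The clock starts at discontinuation: "This parameter is calculated as interval from discontinuation of treatment (including this day"). The event is the first later count below 30 G/L. Two censoring bullets follow:

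- The first bullet covers patients in whom no loss is seen: "If a patient does not loose sustained response the interval is censored with the date of the last platelet assessment".
- The second bullet covers those regarded as never having responded, and sets their duration to zero: "If a patient does not respond initially (i.e. all platelet counts <30 G/L until treatment discontinuation) the interval is censored with 0 (days").

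For the DEX arm, SAP 5.1 fixes the stop date: "the time point of treatment discontinuation is the date of last study medication dexamethasone documented on the" end-of-treatment form. Protocol 6.1 describes the dexamethasone regimen as given "orally at a dose of 40 mg QD for 4 consecutive days at 4 weeks intervals", with intervals of 14 to 28 days also allowed, for one to three cycles. No further course follows once counts exceed 150. On sampling, Protocol 8.3.1 says: "Hematology including platelet counts will be performed at Week 1/Day 1 (baseline) and weekly" for the first four weeks, then every two weeks to Week 33 and every four weeks to Week 53.

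**The concern.** The zero-day bullet is meant for patients who never responded, but it looks only at counts up to the stop date. After one four-day DEX cycle, no post-dose count is scheduled by that date, so the test cannot tell a responder from a non-responder. SAP 5.5.4 and 5.5.5 avoid this by judging initial response up to Week 4; only 5.5.3 ties it to the stop date.

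The same patient could be a responder for the primary endpoint (Protocol 12.4.1, SAP 2.5.1) and contribute zero duration to secondary endpoint 2. The effect would be one-sided. ETB+DEX patients have 26 weeks of on-treatment counts, whereas one-cycle DEX patients include those stopped because their counts exceeded 150, who are among the arm's best responders. Censoring at 0 days removes a patient from every risk set. The remaining DEX curve then rests on patients who did worse.

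**Working it through.** The plan states no figure for this derivation, so there is none to reproduce. The check is a day count followed by an illustration.

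**Inputs.** Visit days come from Protocol Table 8-1, cycle length and interval from Protocol 6.1, the stop date from SAP 5.1, and the visit window (±1 day for weekly visits, ±3 days otherwise) from Protocol section 8.

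**Formulas.** Week w Day 1 = study day 7(w − 1) + 1. Last DEX dose = (cycles − 1) × interval + 4.

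**Scheduled post-baseline counts on or before the stop (nominal days).**

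| Regimen | Stop day | Counts by the stop | Number |
|---|---|---|---|
| DEX, 1 cycle | 4 | none | 0 |
| DEX, 2 cycles, 14-day interval | 18 | 8, 15 | 2 |
| DEX, 2 cycles, 28-day interval | 32 | 8, 15, 22, 29 | 4 |
| DEX, 3 cycles, 14-day interval | 32 | 8, 15, 22, 29 | 4 |
| DEX, 3 cycles, 28-day interval | 60 | 8, 15, 22, 29, 43, 57 | 6 |
| ETB+DEX, 26 weeks | 182 | 8, 15, 22, 29, then every 14 days from 43 to 169 | 14 |

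With the one-day window, the Week 2 visit falls on Day 7 at the earliest, still after Day 4.

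**Applying the rule to one cycle.** The screening count is below 30 by eligibility. If Day 1 is also below 30 and there is no unscheduled count of 30 or more by Day 4, every count up to discontinuation is below 30, whatever happens from Day 8 on. Suppose this patient holds 30 or more to Week 53 Day 1 (Day 365):

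- First bullet: 365 − 4 + 1 = 362 days (362/7 = 51.7 weeks), censored.
- Second bullet: 0 days, censored.

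**Which bullet prevails.** The text does not say. A true non-responder has counts below 30 after the stop and would otherwise be an event. The zero-day bullet therefore changes a result only if it overrides the general rule, and that makes 0 days the natural reading.

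**Size (assumed data).** Take 12 DEX patients: 4 sustained to Day 365, 4 losing response 26, 40, 82 and 138 days after the stop, and 4 never responding (censored at 0 throughout). Let m of the 4 sustained patients be set to 0 days. Then 8 − m patients are at risk at the first loss, and each of the four losses removes one. After day 138 the estimate is the product of (1 − 1/r) for r = 8 − m down to 5 − m, which equals (4 − m)/(8 − m).

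| m | Late estimate | Day the curve first reaches 0.50 or below |
|---|---|---|
| 0 | 4/8 = 0.50 | 138 |
| 1 | 3/7 = 0.43 | 138 |
| 2 | 2/6 = 0.33 | 82 |
| 3 | 1/5 = 0.20 | 82 |
| 4 | 0/4 = 0.00 | 40 |

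**The case against.** The strongest reply is that the first bullet already covers a sustained responder, so the patient keeps the full duration. The bullet does fit, and a reader might wrongly infer that such patients are certain to be set to 0 days. What the text establishes is two conflicting rules without an order, of which the zero-day reading is the more natural. That still needs correcting, because two programmers could produce different curves.

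A second reply is case review. Response and the reasons for non-response are assessed at the Data Review Meeting (SAP 2.5.1, 2.5.4, 5.5.1.1), and the DEX stop date is verified there (SAP 5.1). Setting a patient classed there as a sustained responder to zero would contradict the SAP's own classification. However, 5.5.3 gives a direct calculation and cites no committee decision, whereas 5.5.4 and 5.5.5 do cite one.

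Third, the sentence in SAP 2.7.1 item 2 breaks off before naming the population, so a restriction to responders may exist that cannot be seen. It would not by itself settle how 5.5.3 identifies an initial responder.

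Fourth, patients escape the rule if Day 1 was already 30 or more after pre-treatment, which the rationale for Amendment 2 says happened in some patients, or if an unscheduled count by Day 4 was 30 or more. This limit stands.

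Two wider inferences are tempting but not supported. Multi-cycle patients are not generally affected: they have at least two scheduled counts by their last dose, and the rule reaches them only if every count up to that dose was below 30. Nor does SAP 2.5.4 show a biased table where it lists "Platelet counts at treatment discontinuation: sample statistics". It does not say which sample is used, and that is missing detail rather than a demonstrated error.

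**Conclusion.** The point holds in a limited form. As written, SAP 5.5.3 allows a one-cycle DEX patient with a Day 1 count below 30, and no count of 30 or more by Day 4, to be censored at 0 days despite a response of about 362 days. Under that reading, the DEX curve for secondary endpoint 2 is biased downward and the comparison favours ETB+DEX.

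The size is unknown because the documents do not give the number of one-cycle patients. On the assumed data, the late estimate lies anywhere from 0.50 to 0.00. If no patient is affected, nothing changes. With about 24 patients in total (Protocol 12.8.1), a few could shape the curve.

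The endpoint is secondary, and all analyses are descriptive after Amendment 3. A reader might infer that the primary response rate is distorted too. It is not, because it does not use this derivation.

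**What to change.** Amend SAP 5.5.3 in three respects; dosing is not touched.

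1. **Window.** Apply the zero-day rule only to patients with no count of 30 G/L or more from first dose through a window that includes the first post-cycle counts. One option is 28 days after the start of the last dexamethasone cycle for DEX, and the first count after the last eltrombopag dose for ETB+DEX. For one DEX cycle this brings in Days 8, 15, 22 and 29. Ignore counts after rescue, or after a switch to or re-initiation of eltrombopag, so that a later drug's effect is not credited to study treatment.
2. **Precedence.** State that all other patients follow either the event rule or the first censoring bullet.
3. **Loss.** Count loss of response only after the first count of 30 or more. Otherwise a one-cycle patient with 25 on Day 8 and 80 on Day 15 would be an initial responder with an event on Day 8.

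The cost is two or three SAP sentences and minor programming, with no new samples. The windows differ between the arms, which the SAP should acknowledge.

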#### 5.5.4 Duration of overall response

Overall response (OR) and time points reaching and loosing OR was assessed by the Data Review Committee, see data Review Meeting Minutes.

The following censoring rules are applied:

- If a patient does not loose overall response the duration is censored with the date of the last platelet assessment after Week 4
- If a patient does not respond initially by Week 4 (i.e. all platelet counts <30 G/L until Week 4) the interval is censored with 0 (days)

#### 5.5.5 Duration of complete response

Complete response (CR) and time points reaching and loosing CR was assessed by the Data Review Committee, see data Review Meeting Minutes.

The following censoring rules are applied:

- If a patient does not loose complete response the interval is censored with the date of the last platelet assessment after Week 4
- If a patient does not respond completely initially by Week 4 (i.e. all platelet counts <100 G/L until Week 4) the interval is censored with 0 (days)

#### 5.5.6 Time to platelet count >= 150 G/L

The time to platelet count  $\geq 150$  G/l is calculated as interval from start of study medication to the date when the platelet count was  $\geq 150$  G/L the first time (including unscheduled visits).

The following censoring rules are applied:

- If a patient does not have a platelet count  $\geq 150$  G/L the interval is censored with the date of last platelet measurement

#### 5.6 Rule of exclusion criteria of analysis sets

Table 1	Protocol	deviations	that cause	subjects to	be excluded

Deviation ID	Description of Deviation	Exclusion in Analyses
I01	No informed consent obtained prior to study	Excluded from all analyses
N.a.	Not treated with any study medication	Excluded from SAF population

Table 2	Subject Classification
---------	------------------------

Analysis Set	PD ID that	Non-PD criteria that cause
	cause subjects to be excluded	subjects to be excluded
ENR	I01	Not having informed consent
SAF	NA	Not in ENR;
		Not treated with any study medication

Analysis Set	PD ID that	Non-PD criteria that cause
	cause subjects to be excluded	subjects to be excluded
FAS	NA	Not in ENR;

# 6 Reference

Not applicable.
